Research Summary

1. Protocol Title:

Comparison of TAP, Anterior QL, or ESP Block for Elective Cesarean Section

2. Purpose of the Study:

The purpose of this prospective single center, randomized study is to determine if ultrasound guided Quadratus Lumborum (QL) and Erector Spinae Plane (ESP) blocks decrease opioid consumption compared to Transversus Abdominis Plane (TAP) in subjects undergoing elective cesarean section. Total opioid consumption and pain scores will be monitored for 48 hours postoperatively.

3. Background & Significance:

Cesarean section is an invasive surgery that can lead to significant postoperative pain. Well controlled postoperative pain in this specific patient population can help minimize the effect of surgery on a new mother's ability to care for her newborn and ease the transition back home, as well as allay any concerns regarding transfer of opiates through breastfeeding.

The typical anesthetic plan involves a spinal anesthetic or combined spinal epidural anesthetic as the primary anesthetic for the procedure followed by a combination of oral pain medications, including opioids, to control pain postoperatively. Side effects from opioid use, including nausea, vomiting, sedation, or respiratory depression, can hinder a new mother's ability to fully participate in the care of her newborn. Additionally, some women are leery to take opioids if they are breastfeeding for fear of transfer to their newborn [1]. Despite widespread postoperative prescription of opioids, women report poor pain control after cesarean section [2-4]. As part of a larger public health concern, unused postoperative opioids can be detrimental and the possibility of persistent opioid use after surgery is feasible in this patient population [5].

TAP blocks have been utilized for years to help control incisional pain after abdominal surgeries, including cesarean section [6, 7]. However, it is not without limitations and there is some question regarding efficacy [8]. TAP blocks often decrease somatic pain, but do not impact visceral pain which can contribute to uncontrolled postoperative pain after cesarean section. Additionally, it has been shown that TAP blocks do not improve analgesia when patients are already receiving intrathecal morphine[9].

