Patients who consent to be in this study will be randomized to receive one of three truncal nerve blocks using an online randomization program by the study PI ([name]): (1) ultrasound-guided bilateral classic TAP block; (2) ultrasound-guided bilateral anterior QL (also known as transmuscular or QL type 3) block; (3) ultrasound-guided bilateral ESP block at the level of T9. These nerve blocks will be performed after delivery and within one hour of skin closure with 25 mL of 0.2% ropivacaine with epinephrine 1:400,000 per side. Nerve blocks will be performed by a dedicated and trained group of regional anesthesiologists. This non-blinded regional anesthesiologist will save an ultrasound image after local anesthetic administration while the needle is still in position on each side. The study team will review these images to ensure a high quality of block performance.

Patients will have standard postoperative pain medication orders, including acetaminophen 975 mg PO Q6H for 4 days (scheduled, starting 6 hours after intraoperative rectal dose), ketorolac 15 mg IV Q6H for 24 hours (scheduled, starting 6 hours after intraoperative dose), ibuprofen 600 mg PO Q6H for 3 days (scheduled, starting 24 hours after first dose of ketorolac) and oxycodone 5-10mg PO Q3-4H PRN for 4 days. If patients are unable to tolerate oral medication or oxycodone is insufficient, rescue medications may be ordered: IV morphine 1-2 mg or IV hydromorphone 0.3-0.5 mg Q4H as needed. There is no change from the standard postoperative order sets used for patients after cesarean section.

Subjects' verbal pain scores at rest and with movement as well as opioid consumption will be recorded at 2, 6, 24, and 48 hours postoperatively. The validated Obstetric Quality of Recovery-11 (ObsQoR-11) score will also be assessed at 24 and 48 hours postoperatively [17]. Additionally, the amount of antiemetics and antipruritics used will also be recorded at the above time points. These scores will be entered into a Duke University Hospital REDCap database. Subjects will also be sent a survey assessing their satisfaction with pain control one week after discharge via email or telephone. This information will be collected via Duke University Hospital REDCap.

5. Selection of Subjects:

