Benefits include contributing to general knowledge to improve future patient care. Benefits also include potential analgesic benefit, decreased pain scores, and improved patient satisfaction. Conversely, this study may show no benefit of the block, thereby invalidating the technique.

11. Costs to the Subject:

Subjects will not incur any additional costs to participate in the study. A MaestroCare build will be created to ensure that any subjects are not charged for researched related procedures, equipment, or medications.

12. Data Analysis & Statistical Considerations:

A randomized trial of 75 subjects (25 per group) will provide 80% power to detect a 35% decrease in opioid use between treatment groups in a t-test at an alpha level 0.017 utilizing Bonferroni's correction,

(parametric), Mann-Whitney U Test (nonparametric), or repeated measures ANOVA as appropriate. Sample size and power calculations were performed using PASS v15 (NCSS, LLC. Kaysville, Utah).

Patient and surgical characteristics will be summarized by standard descriptive statistics and will be compared between groups using t-tests, ANOVA, or Wilcoxon sum ranked tests as appropriate. We will report odds ratios, 95% confidence intervals, and p-values to assess significance and clinical importance of the observed treatment effect. Additional measures of treatment efficacy (pain scores, ease of mobility, overall pain experience) will be summarized overall and between groups to further characterize the treatment effect in this population.

13. Data & Safety Monitoring:

In accordance with federal regulations the PI will monitor for, review, and promptly report to the IRB, appropriate institutional officials, sponsor, coordinating center and the appropriate regulatory agency head all unanticipated problems involving risks to subjects or others that occur in the course of a subject's participation in a research study (45 CFR 46.103(b)(5)(i) and 21 CFR 56.108(b)(1)), all AE reports will be reported per the DUHS IRB policies. PI will be monitoring all AEs and submitting reports to the IRB per DUHS IRB policy.

14. Privacy, Data Storage & Confidentiality:

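### The odds ratio is the only effect measure visible in Section 12, but the trial is powered on a 35% decrease in an amount of opioid, with which an odds ratio cannot be compared directly (minor)

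*Combined protocol and SAP*

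**What the plan says.** All statistical text is in Section 12 (Data Analysis & Statistical Considerations).

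- **Power.** 75 subjects, 25 per group, are said to give "80% power to detect a 35% decrease in opioid use between treatment groups in a t-test at an alpha level 0.017 utilizing Bonferroni's correction".
- **Tests.** The text breaks off after the Bonferroni clause and resumes at "parametric), Mann-Whitney U Test (nonparametric), or repeated measures ANOVA as appropriate". Words are lost between the two.
- **Reporting.** "We will report odds ratios, 95% confidence intervals, and p-values to assess significance and clinical importance of the observed treatment effect".
- **Other outcomes.** The next sentence says: "Additional measures of treatment efficacy (pain scores, ease of mobility, overall pain experience) will be summarized overall and between groups".

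The outcome behind the power statement is described elsewhere. Section 2 (Purpose of the Study) asks whether QL and ESP "blocks decrease opioid consumption compared to Transversus Abdominis Plane (TAP) in subjects undergoing elective cesarean section" and says that total consumption is followed for 48 hours. Section 4 (Design & Procedures) adds that "opioid consumption will be recorded at 2, 6, 24, and 48 hours postoperatively". No visible text defines a yes/no opioid outcome, a cut-point, or a logistic or ordinal model. None names a mean difference, percentage reduction or shift as the estimate.

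**The concern.** The reporting sentence promises to judge clinical importance. The only benchmark for that in the documents is the 35% decrease, which is a relative change in a mean amount. The one effect measure visible beside that promise is on a different scale. To obtain an odds ratio for opioid consumption, the analyst must choose a cut-point or fit an ordinal model, and the visible plan fixes neither. The choice could then be made after the data are seen. A reader given only the odds ratio could not tell whether the planned decrease was reached.

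A smaller point concerns the intervals. The only stated test level is 0.017, while the intervals are 95% and are offered partly to assess significance. When p lies between 0.017 and 0.05, the 95% interval excludes no effect although the corrected test does not reject. Without a label, such an interval could be misread as a significant result.

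**Working it through.** **Inputs from Section 12:** 25 per group, 80% power, 35% decrease, t-test, alpha 0.017. Since 0.05/3 = 0.0167, three pairwise comparisons are inferred; the visible text does not give their number.

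**Assumptions (not in the documents):** normal data, equal SDs, a two-sided test, and the decrease measured against the TAP mean. No mean or SD is given, so the 80% cannot be reproduced independently. It can only be solved backwards for the SD it implies.

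**Step 1: SD implied by the power claim.** Take the noncentral t distribution with 48 df and noncentrality d × √(25/2). The critical value at two-sided 0.017 is 2.473. Power of 80% requires d = 0.941. The SD as a fraction of the TAP mean is therefore 0.35 / 0.941 = 0.372, or 37%. If the 0.017 test is one-sided, d = 0.858 and the SD is 0.35 / 0.858 = 0.408, or 41%.

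**Step 2: odds ratios for the same 35% decrease.** Suppose, for illustration only, that opioid use were split at the TAP percentile with standard normal value z. The proportion above the cut is p0 = 1 − Φ(z) with TAP and p1 = 1 − Φ(z + 0.941) in the comparison arm. The odds ratio is [p1/(1 − p1)] / [p0/(1 − p0)].

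| Cut (TAP percentile) | p0 | p1 | Odds ratio |
|---|---|---|---|
| 10th | 0.90 | 0.633 | 0.19 |
| 25th | 0.75 | 0.395 | 0.22 |
| 50th | 0.50 | 0.173 | 0.21 |
| 75th | 0.25 | 0.053 | 0.17 |
| 90th | 0.10 | 0.013 | 0.12 |

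Worked row at the median: (0.173/0.827) / (0.5/0.5) = 0.21. One 35% decrease thus gives odds ratios from 0.12 to 0.22 according to the cut alone. With lognormal data at the same SD and a mean ratio of 0.65, the range is 0.06 to 0.14.

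**Step 3: an odds ratio without a cut.** A generalised odds ratio, P(treated > TAP) / P(treated < TAP), can be derived from the Mann-Whitney statistic. Under the same model P(treated > TAP) = Φ(−0.941/√2) = 0.253, so the ratio is 0.253/0.747 = 0.34. This is another value for the same 35% decrease.

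**Step 4: interval level.** With 48 df the multiplier is 2.011 for a 95% interval and 2.473 for a 98.3% interval; 2.473/2.011 = 1.23. As a fraction of the TAP mean, the half-width is multiplier × 0.372 × √(2/25):

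- 95%: 2.011 × 0.372 × 0.283 = 0.21
- 98.3%: 2.473 × 0.372 × 0.283 = 0.26

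At this SD, an observed decrease between about 21% and 26% would have a 95% interval that excludes no effect without meeting the 0.017 threshold.

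**The case against.** **Lost text.** The missing words sit in the sentence that links the opioid target to its tests. They may name a binary outcome, a mean difference or a time point. This stands, and it limits the point to the visible text. A reader might infer that the plan omits a mean difference altogether; the documents cannot support that. The reporting sentence itself is complete, however, and a binary outcome named in the gap would still not put an odds ratio on the scale of a 35% decrease in an amount.

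**Meaning of the treatment effect.** The reporting sentence names no outcome, follows one on patient and surgical characteristics, and could be generic reporting text. That is fair. A reader might infer that opioid use is to be dichotomised, but nothing says so. The reading used here rests on the stated aim and on the next sentence, which sets pain scores, mobility and pain experience apart as additional measures.

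**Odds ratios from the listed tests.** It would be too strong to say that none of the listed tests can lead to an odds ratio. Mann-Whitney yields a generalised odds ratio and is closely related to the proportional-odds model. The visible plan names neither, and neither maps to one percentage decrease.

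**Realism of the illustration.** No cut appears in the plan. At the implied SD the range under normality is modest, and the normal model puts about 4% of treated values below zero (Φ(−0.65/0.372) = 0.04). The figures show that the scales do not match; they do not show damage to the trial's conclusions.

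**Interval level.** Unadjusted 95% intervals beside a Bonferroni-corrected test are ordinary reporting. A reader might infer that they undo the correction. The documents do not support this, because the intervals are never named as the decision rule and the p-values can be held against 0.017.

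**Conclusion.** The point holds as a minor correction. The only effect measure visible in Section 12 does not fit the outcome on which the trial is powered. An odds ratio needs a cut-point or ordinal model that is not visible, and it cannot be compared directly with the 35% decrease. At the implied SD of 37% of the TAP mean, the same decrease corresponds to odds ratios from 0.12 to 0.22 across cuts. If the 0.017 test is one-sided (SD 41%), the value at a median cut is 0.24 instead of 0.21. These figures rest on normal data, equal SDs and an SD solved back from the power claim.

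The trial is not compromised: consumption is recorded as an amount, and group means can still be computed. What is missing from the visible text is a commitment to report their difference. The interval level is a labelling matter only.

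**What to change.** Replace the reporting sentence in Section 12 with:

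> For each pairwise comparison of opioid consumption we will report the difference in means, also expressed as a percentage of the TAP mean for the two comparisons with TAP (or the Hodges-Lehmann shift if Mann-Whitney is used), with a confidence interval and a p-value judged against 0.017. Odds ratios will be reported only for explicitly defined binary outcomes.

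Then settle the interval level in one of two ways:

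- give 98.3% intervals, which match the 0.017 test; or
- keep 95% intervals, labelled as unadjusted and not used to declare significance.

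**Cost.** A few sentences of text; sample size, tests, alpha and data collection stay as they are. The 98.3% option makes intervals about 23% wider (half-width 26% instead of 21% of the TAP mean at the implied SD). Labelling the 95% intervals costs nothing.

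**Limits.** The percentage is a point value without its own interval. The wording names no time point, because the visible text designates none for the test, and it does not set the estimate for a repeated measures ANOVA. If the complete text of Section 12 already covers any of this, the replacement should be aligned with it.
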